Appendix 3. IMPROVE Pilot Randomized Controlled Trial Detailed Methodology and Analyses

1.0 Overall study design:

The IMPROVE-Pilot Study is a single-centre, single-blind, parallel, randomized controlled trial with a one-to-one intervention to control allocation.

2.0 Participants Eligibility Criteria:

2.1 Inclusion Criteria: Participants must meet all of the following:

- a) adult women aged 18 years or older;
- b) diagnosis of a HDP (i.e., preeclampsia, eclampsia or gestational hypertension);
- c) delivering at The Foothills Medical Centre (FMC) in Calgary, Alberta;
- d) ability to read, write, understand, and provide informed consent in English; and
- e) have telephone access.

Justification: Telephone access is integral to the implementation of the study intervention as a component of the counselling intervention. Although 90% of Canadians report access to a cellular phone, the number of women who do have telephone access will be assessed in order to ensure no evidence of selection bias¹.

2.2 Exclusion Criteria: Individuals with any of the following will be excluded:

- a) pre-existing vascular disease (coronary artery disease [i.e., stable angina, unstable angina, myocardial infarction, percutaneous coronary intervention or coronary artery bypass surgery], cerebrovascular disease [i.e., ischemic stroke or transient ischemic attack], or peripheral arterial disease [i.e., known abnormal ankle-brachial indices, symptoms of intermittent claudication, or bypass surgery to the extremities]);
- b) chronic hypertension;
- c) diabetes (type 1 or type 2);
- d) pre-pregnancy kidney disease;
- e) planning another pregnancy within one year;
- f) counselling may not be appropriate (i.e., impaired cognition);
- g) live more than 200 km outside the Calgary region; and
- h) planning to move outside the Calgary region within one year of randomization.

Justification: The above medical conditions are excluded, as there already are either existing recommendations for vascular prevention (e.g., use of specific pharmacotherapy) or lifestyle programs available (e.g., diabetes). This study will exclude women who are planning a pregnancy within one year, as the study intervention is a full-year duration and weight loss during pregnancy remains controversial². This is unlikely to reduce study recruitment or affect external generalizability, as obstetrical societies recommend spacing pregnancies by at least eighteen months to two years to minimize preeclampsia recurrence³

3.0 Planned trial interventions:

3.1 Intervention: In addition to standard care, participants randomized to the intervention arm will also receive the CardioPrevent® Program. This is a 1-year, evidence-based behaviour change lifestyle program that consists of 25 contacts (in person, by phone and in groups) with a trained lifestyle counsellor to facilitate desired lifestyle behaviours within the participants' own social context.

3.2 Control: Standard postpartum clinical care through the participants' usual healthcare providers.

3.3 All Participants: Participants in both arms will receive educational material about the risk of CVD, and CVD prevention for women with HDP from the Preeclampsia Foundation (*Appendix 6*).

3.4 Duration of Treatment: The treatment period is one year. This duration is clinically important for two reasons. First, longer behaviour change interventions have greater success with maintenance of healthy behaviours compared with shorter interventions⁴. Thus, the CardioPrevent® behaviour change

intervention was specifically designed to be one year⁵. Second, maternity leaves in Canada are generally one year. Women in the intervention arm will be in the “relapse prevention” phase of the behaviour change intervention as they return to work. The CardioPrevent® postpartum participants to date have emphasized the importance of this phase.

3.5 Duration and frequency of follow up: All study participants will complete in person clinical assessments at baseline, six months, and one year after their randomization date. All study assessments will be done on an individual basis, by a research assistant who is blinded to group assignment.

4.0 Study Outcomes:

4.1 Primary outcome:

a) *Study feasibility:* Acceptance of the study by women with HDP (i.e., feasibility) measured by all of the following: recruitment rate of $\geq 20\%$ over a 6-month time period (as per weekly recruitment logs –); participant adherence of $\geq 80\%$ to the lifestyle program (i.e., 20/25 contacts with counsellor completed); overall study completion rate of $\geq 75\%$ of participants; and participant satisfaction score of \geq fair on the Client Satisfaction Questionnaire at the end of study⁶.

b) *Implementation and fidelity of CardioPrevent® at a second centre* measured by standardized audits as well as similar clinical outcomes between sites

4.2 Secondary outcomes:

a) Comparison of the following *clinical outcomes* between both study arms at one-year of follow-up: weight, body mass index, waist-to-hip ratio, smoking status, postpartum depression, blood pressure, fasting lipids, fasting glucose, HbA1C, urine albumin to creatinine ratio, metabolic syndrome z-score and CVD risk.

b) *Microvascular function:* mean changes from baseline to one year of follow-up compared between groups for the following measures: flow mediated dilatation (FMD), brachial artery hyperemic velocity and peripheral arterial tonometry (PAT).

c) Changes in physical activity and dietary behaviour.

4.3 Measurement of study outcomes: Standardized assessments will be performed by a trained research assistant (blinded to group allocation) as outlined below, and in the Schedule of Measures (Appendix 8).

4.3.1 Clinical measures:

a) *Blood pressure:* Blood pressure is measured in a seated position after a five-minute rest period using an automated non-invasive blood pressure monitor (BPTru®) that automatically performs up to six measurements, discards the first reading, and displays the average of the subsequent readings⁷. Treatment of hypertension is determined by a review of current medication use.

b) *Body composition:* Height and weight are measured for the determination of body mass index (BMI) using a standardized protocol⁸. Waist and hip circumferences are measured using standard anatomical landmarks following the World Health Organization’s recommendations⁹.

c) *Smoking status:* Current smokers are defined as individuals who have smoked any cigarettes (even a puff) in the past seven days¹⁰. Claims of non-smoking are verified using a carbon monoxide analyzer (Bedfont Smokerlyser) with CO levels $< 10\text{ppm}$ confirmatory for non-smoking¹¹.

d) *Medication Use:* It is measured by having participants list the name and dosage of all prescription medications they are currently taking. Participants are asked to bring their medications with them to each visit for verification. Medication adherence with MAQ-8 questionnaire¹².

e) *Metabolic Syndrome:* Using the ATP III Criteria for Metabolic Syndrome, all five variables (i.e., waist circumference $\geq 88\text{cm}$; triglycerides $\geq 1.7\text{ mmol/L}$; HDL $< 1.3\text{ mmol/L}$; BP $\geq 130/\geq 85\text{ mmHg}$; and fasting glucose $\geq 6.1\text{ mmol/L}$) will be recorded categorically¹³ and also scored as a continuous variable as a z-score (a measure of overall CVD risk) in lifestyle intervention studies¹⁴⁻¹⁶.

f) *Breastfeeding / Infant Feeding:* will be self-reported and categorized as: no breastfeeding or expressed breast milk (EBM); breastfeeding/EBM and formula, exclusive breast milk. The duration

of breastfeeding will also be reported for use in statistical analyses given the effects of lactation on vascular health^{17, 18}.

4.3.2 Laboratory measurements:

- a) *Fasting blood tests:* Will be collected after a minimum 8-hour fast. Plasma lipids (total cholesterol [TChol], HDL-C, LDL-C, triglycerides, calculated TChol to HDL ratio), creatinine, glucose and HbA1C will be analysed using standardized laboratory procedures at the FMC lab¹⁹.
- b) *Urine tests:* A random urine sample will be analysed for the albumin to creatinine ratio.

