5.7 Anticipated loss to follow-up: In the Family Heart Health Study (non-postpartum individuals), at one year, the rate of loss to follow-up was 27% in the standard care arm and 24.6% in the intervention arm (25% cited "too busy" or "not interested")³⁴. In the DEBI postpartum trial, however, there were higher rates of participant completion of the 1-year study: 90% in the intervention arm and 80% in the control arm; and 97% of participants in the intervention arm were "satisfied" with the program³⁵. Thus the target participant completion rate for the IMPROVE-Pilot study is $\geq 80\%$ (i.e., LTFU of <20%). To reach this target, we have also included reimbursements for parking and childcare costs for the baseline, 6- and 12-month outcome assessment visits. In addition, we have increased the study sample size by 30% to account for potential LTFU common to lifestyle intervention studies³⁴.

5.8 Sample size: A total of 84 women will be recruited (42 in each arm). This is based upon a minimally clinically important difference in BMI of 1 kg/m² supported by the literature on the association between BMI and CVD^{36, 37} and by the finding from the Canadian PE-NET cohort demonstrated that women with HDP actually increase their BMI by 1 year postpartum³⁸. Results of CardioPrevent® in other populations of women resulted in SD of 1.4-2.3³⁴. The lower SD of 1.4, alpha of 0.05 and power of 80% yields 32 women per arm (64 total). We increased this by 30% to account for loss to follow-up in other postpartum studies³⁵.

5.9 Recruitment: There are over 7000 deliveries per year at the FMC. Using a conservative estimate of 7% prevalence of HDP (as it is a tertiary care referral centre), approximately 245 women (10 per

week) will have HDP over our 6-month recruitment period. We anticipate recruiting 2-3 eligible women per week to reach our target sample size in 6 months. Recruitment will be monitored on a weekly basis with review of recruitment logs that monitors reasons for non-participation and ineligibility. Should recruitment rates from the in-patient wards alone be below anticipated targets, we will engage alternate modes of participant recruitment through outpatient clinics (Maternal Fetal Medicine and Obstetric Medicine) where we have co-investigators and recruitment infrastructure.

6.0 Statistical analyses: At the end of the study, the following will be analyzed.

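### The 20% recruitment criterion in the primary outcome does not fit the protocol's own figures: 84 women in 6 months needs about 34% of women with HDP, and 20% is about 49 women

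*Protocol*

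**What the plan says.** Section 4.1(a) defines the primary feasibility outcome as "Acceptance of the study by women with HDP (i.e., feasibility) measured by all of the following". The first of the four listed components is a "recruitment rate of $\geq 20\%$ over a 6-month time period", taken from the weekly recruitment logs. The others concern adherence to the programme, study completion and satisfaction. The section does not say whether the 20% is a share of all women with HDP, of eligible women or of women approached. Nor does it say whether a woman counts as recruited at consent or at randomisation.

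Section 5.8 fixes the sample: "A total of 84 women will be recruited (42 in each arm").

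Section 5.9 gives the pool. It starts from "There are over 7000 deliveries per year at the FMC" and, "Using a conservative estimate of 7% prevalence of HDP", arrives at "approximately 245 women (10 per" week) who "will have HDP over our 6-month recruitment period". It then expects two to three eligible women a week to be enough to reach the target within the 6 months. If the wards fall short, outpatient clinics are the fallback: "Should recruitment rates from the in-patient wards alone be below anticipated targets, we will engage alternate modes of participant recruitment".

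**The concern.** The threshold, the pool, the target and the period are all fixed in this one document, and they do not fit together. The criterion is a decision threshold in the primary outcome, and it covers the same 6 months in which section 5.9 expects the full sample to be reached. A reader of the results would naturally take a met recruitment criterion to mean that a trial of this size can be recruited in the planned time. On the protocol's own figures it would not mean that. Nothing in the document links the 20% to the 84 or explains the distance between them.

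**Working it through.** **Inputs.** From section 5.9: 7000 deliveries per year (given as a lower figure), HDP prevalence 7%, a recruitment period of 6 months (26 weeks), and an expected pace of 2 to 3 women per week. From section 5.8: target 84, built from 32 per arm plus 30%. From section 4.1(a): threshold 20%.

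**1. Reproduce the protocol's own figures.**
- Pool: 7000 × 0.07 × 6/12 = 245. This agrees. Per week it is 245/26 = 9.4, which the protocol rounds to 10.
- Sample size: a two-sample t-test for a difference of 1 kg/m², SD 1.4, two-sided alpha 0.05 and 80% power needs 31.8, so 32 per arm. Then 32 × 1.3 = 41.6, so 42 per arm and 84 in total. This agrees.

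**2. What the target needs.**
- Share of all women with HDP: 84/245 = 34.3%.
- Pace: 84/26 = 3.23 women per week.

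**3. What the criterion delivers.**
- 0.20 × 245 = 49 women, or 49/26 = 1.9 per week.
- 49/84 = 58% of the target.
- At that pace, 84 women would take 84/(49/26) = 44.6 weeks rather than 26.

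**4. Sensitivity to the pool and the denominator.**
- With the rounded 10 per week, the pool is 260. Then 20% is 52 women, and 84 needs 84/260 = 32.3%.
- If the denominator is eligible women, the eligible share is needed, and the protocol does not give it. Assuming 50% to 90% of the 245:

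| Eligible share (assumed) | Eligible women | 20% of them | Rate needed for 84 |
|---|---|---|---|
| 90% | 220.5 | 44 | 38% |
| 70% | 171.5 | 34 | 49% |
| 50% | 122.5 | 24.5 | 69% |

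- For 20% to yield 84, the pool would have to be 84/0.20 = 420 women with HDP in 6 months. That is 420/245 = 1.7 times the stated figure, or a prevalence of 420/3500 = 12% at 3500 deliveries per half-year.

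**5. The pace in section 5.9.**
- 2 × 26 = 52 and 3 × 26 = 78. These are 21% and 32% of 245.
- Even the upper end of the expected pace falls short of 84, although the section says this pace reaches the target.

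**The case against.** The strongest reply is that a feasibility threshold is a floor and not a forecast. Section 4.1(a) describes acceptance by women with HDP, which is an uptake proportion, while section 5.8 sets the number to enrol separately. A floor may properly lie below the planned rate. The 20% also has a visible origin: two of ten women per week is the lower end of the pace in section 5.9. All of this stands, and it is why the threshold is not wrong merely for being below 34%. What remains is that the protocol does not present 20% as a floor, does not justify it, and does not say what meeting it would show.

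A second reply is that 245 is deliberately conservative and the denominator is unstated, so 49 is not a fixed number. That is fair, but the direction does not depend on it. The pool would have to be 1.7 times larger to close the gap, and an eligible-only denominator widens it.

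Some stronger readings are tempting but not supported:
- *That outpatient recruits inflate the rate when the wards fail.* Every participant must deliver at the study hospital (section 2.1(c)), and screening is meant to cover all women delivering there (section 5.6). A woman found through a clinic therefore already belongs to the 245 if she delivers in the same period.
- *That the trial would stop at 49 women and lose its power.* No passage closes enrolment at 6 months short of 84, and section 5.9 provides weekly monitoring and a fallback source. The BMI difference behind the 84 concerns a secondary outcome, and section 6.0 calls the comparison of clinical outcomes between arms exploratory.
- *That the study could be declared feasible on 49 women alone.* Recruitment is one of four criteria that must all be met.

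**Conclusion.** The point holds in a limited form. The recruitment component of the primary outcome can be met by about 49 women in 6 months, 58% of the 84 planned for that time, whereas the plan needs 34% of women with HDP. Meeting it is therefore not evidence that the 84-woman design can be recruited on schedule. The figure of 49 assumes the pool of 245 and a denominator of all women with HDP, which is the most favourable reading of that pool. Narrowing the denominator to eligible women lowers the count to between about 25 and 44 if 50% to 90% are eligible (an assumption).

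This should be fixed but is not critical. It does not bias the randomised comparison, and a shortfall against 84 would show in the reported participant numbers. It does affect what a result on the primary outcome can be taken to mean.

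**What to change.** In section 4.1(a):
- State the denominator (all women with HDP who deliver in the 6-month period, or the eligible ones among them).
- Count women at randomisation. Under section 5.1, consent is taken before discharge and randomisation follows at the baseline visit, 6 to 12 weeks postpartum, so a count of consents could exceed the number randomised.
- Then choose one of two courses. Either align the threshold with the target, at about 34% of women with HDP or the matching share of eligible women. Or keep 20% as an explicit minimum-uptake floor, say that it corresponds to about 49 women in 6 months if the denominator is all women with HDP, and say that meeting it does not show that 84 can be recruited in that time.

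In section 5.9, reconcile the expected pace with the target: 2 to 3 per week gives 52 to 78 women in 26 weeks, and 84 needs about 3.2 per week.

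The cost is protocol wording only. The price of the first course is a stricter criterion that the pilot may miss, with no margin below the target. The price of the second is a less favourable stated meaning for the 20%.

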4.3.3 Questionnaires: will be used to measure the following

- a) *Postpartum Depression:* The Edinburgh Postnatal Depression Scale^{20, 21}.
- b) *Diet:* The REAP (Rapid eating assessment of patients)²² and three days of prospective food logs²³.
- c) *Physical Activity:* the IPAQ-short form²⁴, activity logs²⁵, and by accelerometers²⁶.
- d) *Participant Satisfaction:* the Perceived efficiency in patient-physician interaction scale²⁷.
- e) *Social Support:* Multidimensional scale of perceived social support²⁸ and perceived stress scale²⁹.

4.3.4 Cardiovascular Risk: will be measured using the Lifetime Cardiovascular Risk Score³⁰.

4.3.5 Microvascular Function: These tests will be performed by an experienced technician and [name] (PhD Student) in the experienced [name] Lab (Mozell Vascular Function Lab) at the University of Calgary using standardized techniques³¹. Participants will be asked to abstain from caffeine or nicotine for at least 2 hours prior to the testing. Participants will then rest in a temperature-controlled room (22 degree Celsius) for 15 minutes prior to beginning the protocol³¹.

- a) *Flow Mediated Dilatation (FMD)* of the right brachial artery: Using Philips IE 33 (high resolution > 10 MHz linear array ultrasound probe), B mode imaging and pulsed wave Doppler are used to measure the brachial artery diameter at baseline and after 5 minutes of occlusion. For the occlusion, a blood pressure cuff will be placed on the arm above the antecubital fossa with a five minute occlusion time (cuff inflated to 50 mmHg above the participant's systolic blood pressure). Doppler recordings include 15 seconds before and after the cuff pressure is released. Of note, the sublingual nitroglycerine response will not be assessed due to unclear safety of nitroglycerine in lactation.
- b) *Hyperemic velocity (HV):* As part of the FMD testing, hyperemic velocity will be measured for 30 seconds after cuff pressure is released. This is determined by the peak of the velocity-time integral after the first complete velocity envelope. Of note, higher values represent better microvascular dilatation.
- c) *Peripheral Arterial Tonometry (PAT):* PAT consists of measurement of pulse wave amplitude responses using a finger tip (right and left index finger) plethysmographic device (Itamar-medial Inc., Caesaria, Israel).

5.0 Methodology:

5.1 Participant allocation and randomization: In order to maximize recruitment rates, a research nurse at FMC will screen admitted patients on the obstetrical wards for eligibility for the trial prior to discharge from hospital. The research nurse will then approach women who meet the eligibility criteria to explain the study and determine whether the women are interested in participating in the study. If a woman is interested, she will be provided with written information on the study. After providing informed consent, she will be given an appointment for the baseline assessment at approximately six weeks (range of 6 to 12 weeks) postpartum. After discharge from the hospital, participants will be sent reminder information about the study and the date of the baseline visit.

At the baseline assessment visit, consecutive women will be randomized to either the intervention or control arm in a 1:1 allocation, with use of permuted blocks of variable length (2, 4 or 6) using an on-line central randomization system through the Data Management Services group at the Libin Cardiovascular Research Institute. The on-line randomization program will ensure participant eligibility and maintain concealment of allocation. The randomization schedule will be prepared by an independent statistician using a computer-generated random number scheme.

5.2 Blinding - the outcome assessor and statistician: The nature of the intervention (i.e., the CardioPrevent® cognitive-behavioural lifestyle counsellor) does not lend itself to blinding of the participant. However, the research assistant responsible for the outcome assessments will be blinded to each participant's group allocation and will be instructed not to ask any questions pertaining to the study intervention. The study statistician will also be blinded to group allocation.

5.3 Contamination: Contamination is unlikely, as individuals allocated to the control group will not have direct access to the cognitive-behavioural lifestyle counsellor. It is possible, however, that participants may know other women involved in the study. Consequently, participants in both arms will also be instructed not to share their study information with other participants.

5.4 Co-interventions: As participants will know their allocated group, they may relate this information to their usual healthcare providers. It is therefore possible that, if in the control group, the participants' healthcare providers may provide additional lifestyle modification recommendations. Based upon the research of two co-investigators, this is unlikely to have a great effect on the study results, as few healthcare professionals (<10%) counsel women with HDP on future chronic disease risk³², and physicians generally spend less than 8 minutes counselling patients on CVD³³. To further limit this potential bias, information on HDP and CVD will be provided to participants in both arms at the end of the study. Co-interventions with other drug, medical or dietary therapies will be at the discretion of the participant's usual healthcare provider and will be measured and compared in both groups. While the PreVASC clinic (a postpartum vascular prevention clinic) exist for women with HDP in Calgary, as this is not standard care across Canada, in order to minimize bias from the effect of the clinic itself, clinicians will be asked not to include trial participants in PreVASC until study completion. Furthermore, an environmental scan of resources in Calgary yielded no specific lifestyle programs for postpartum women with HDP.

5.5 Adherence / Attrition: All attempts will be made to ensure complete follow up by all participants through in-person, telephone, and email reminders. To increase attendance at scheduled follow-up visits, we will provide reimbursements for parking and childcare costs (if needed), and include only women who live in the immediate Calgary region.

5.6 Selection bias: To minimize selection bias, a standardized systematic process for screening all women delivering at FMC for eligibility will be implemented. Specific reasons for non-participation will be recorded (ineligibility and main reason for declining). In addition, pragmatic eligibility criteria were developed to ensure external generalizability.

5.7 Anticipated loss to follow-up: In the Family Heart Health Study (non-postpartum individuals), at one year, the rate of loss to follow-up was 27% in the standard care arm and 24.6% in the intervention arm (25% cited "too busy" or "not interested")³⁴. In the DEBI postpartum trial, however, there were higher rates of participant completion of the 1-year study: 90% in the intervention arm and 80% in the control arm; and 97% of participants in the intervention arm were "satisfied" with the program³⁵. Thus the target participant completion rate for the IMPROVE-Pilot study is $\geq 80\%$ (i.e., LTFU of <20%). To reach this target, we have also included reimbursements for parking and childcare costs for the baseline, 6- and 12-month outcome assessment visits. In addition, we have increased the study sample size by 30% to account for potential LTFU common to lifestyle intervention studies³⁴.

5.8 Sample size: A total of 84 women will be recruited (42 in each arm). This is based upon a minimally clinically important difference in BMI of 1 kg/m² supported by the literature on the association between BMI and CVD^{36, 37} and by the finding from the Canadian PE-NET cohort demonstrated that women with HDP actually increase their BMI by 1 year postpartum³⁸. Results of CardioPrevent® in other populations of women resulted in SD of 1.4-2.3³⁴. The lower SD of 1.4, alpha of 0.05 and power of 80% yields 32 women per arm (64 total). We increased this by 30% to account for loss to follow-up in other postpartum studies³⁵.

5.9 Recruitment: There are over 7000 deliveries per year at the FMC. Using a conservative estimate of 7% prevalence of HDP (as it is a tertiary care referral centre), approximately 245 women (10 per

week) will have HDP over our 6-month recruitment period. We anticipate recruiting 2-3 eligible women per week to reach our target sample size in 6 months. Recruitment will be monitored on a weekly basis with review of recruitment logs that monitors reasons for non-participation and ineligibility. Should recruitment rates from the in-patient wards alone be below anticipated targets, we will engage alternate modes of participant recruitment through outpatient clinics (Maternal Fetal Medicine and Obstetric Medicine) where we have co-investigators and recruitment infrastructure.

6.0 Statistical analyses: At the end of the study, the following will be analyzed.

Participant characteristics will be summarized with standard descriptive statistics. *Feasibility outcomes* will be summarized as frequencies with % and presented as per CONSORT Guidelines³⁹, between group differences will be tested using Pearson's chi-square or Fisher's exact test. Non-adherence patterns will be assessed. *Quality assurance (QA) measures:* Mean with standard deviation (SD) scores from the three QA checks per counsellor will be compared to Ottawa standards using a Student's t-test. *Clinical outcomes:* Changes from baseline will be summarized using: means with SD; medians with interquartile ranges; and counts with % where appropriate. Exploratory analysis comparing outcomes between arms will be done with T-tests for continuous variables and chi-square or Fisher's exact tests for categorical variables. *Planned subgroup analysis:* will be performed to compare severity of HDP (gestational HTN, non-severe preeclampsia [PE], early onset PE < 34 weeks, or clinically severe PE) on clinical and vascular outcomes. An *intention-to-treat* principle will be followed. All *P-values* will be two-sided, at a significance level of 0.05. *Missing data* will be imputed.

7.0 Trial Management:

The trial will be managed through the Libin Cardiovascular Institute. A 0.4 FTE Research Coordinator will be responsible for the day-to-day conduct of the trial under the supervision of the study PI, including: REB applications; recruitment reports; and data quality reviews. A 0.1 FTE Research Nurse responsible for screening participants and obtaining informed consent. Data will be managed by Libin's Data Management Service, including: development of database; development of electronic case report forms; on-line randomization; and data maintenance and storage.

8.0 References:

1. Quorus Consulting Group. Cell phone consumer attitude study, prepared for the Canadian wireless telecommunications association. 2012;Jan 4 2012.
2. National Research Council. Weight gain during pregnancy: Reexamining the guidelines. *Washington DC: The National Academies Press.* 2009.

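### Section 5.9 says 2-3 women per week reaches the target in 6 months, but that pace gives 52-78 women against the 84 of section 5.8

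*Protocol*

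**What the plan says.** Section 5.8 fixes the target: "A total of 84 women will be recruited (42 in each arm"). It derives this from a BMI difference of 1 kg/m²: "The lower SD of 1.4, alpha of 0.05 and power of 80% yields 32 women per arm (64 total"), raised by 30% for loss to follow-up.

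Section 5.9 describes the supply of patients. "There are over 7000 deliveries per year at the FMC", and a 7% prevalence of hypertensive disorders of pregnancy (HDP) gives about 245 women, put at 10 per week, who "will have HDP over our 6-month recruitment period". The forecast follows: "We anticipate recruiting 2-3 eligible women per week to reach our target sample size in 6 months".

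The same section sets up oversight: "Recruitment will be monitored on a weekly basis with review of recruitment logs". It also names a fallback through outpatient clinics: "Should recruitment rates from the in-patient wards alone be below anticipated targets".

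Two other places matter. Section 4.1a makes a recruitment rate of at least 20% over 6 months, taken from the weekly logs, one component of the primary feasibility outcome. Section 5.1 has women consent on the ward but randomises them only at the baseline visit, 6 to 12 weeks postpartum.

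**The concern.** Rate, period and target are three linked numbers, and any two fix the third. Here they do not agree: no rate within the stated range gives 84 women in the stated period.

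In many trials a loose accrual forecast would hardly deserve comment. In this one, recruitment over 6 months is itself part of the primary outcome, the logs are reviewed weekly, and 2-3 per week is the only weekly recruitment figure given. A team that compares its logs with that figure could be exactly on pace and still be heading for a sample smaller than planned, or for a recruitment period longer than stated.

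**Working it through.** **Inputs.** Target 84, or 42 per arm (section 5.8). Pace 2-3 per week and period 6 months (section 5.9). Difference 1 kg/m², SD 1.4, alpha 0.05, power 80%, inflation 30% (section 5.8); two-sided testing (section 6.0). Deliveries 7000 per year and prevalence 7% (section 5.9). Six months is taken as 26 weeks.

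**The protocol's other figures reproduce.**
- Sample size: a two-sample t-test needs 31.8 per arm, so 32. Then 32 × 1.3 = 41.6, so 42 per arm and 84 in total.
- Pool: 7000 × 0.07 / 2 = 245 women in 6 months, or 245/26 = 9.4 per week, which the protocol rounds to 10.

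**The pace does not.** Women recruited = weekly rate × weeks.

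| Rate per week | Women in 26 weeks | Short of 84 | Weeks to reach 84 |
|---|---|---|---|
| 2 | 2 × 26 = 52 | 32 | 84/2 = 42 |
| 2.5 | 2.5 × 26 = 65 | 19 | 84/2.5 = 33.6 |
| 3 | 3 × 26 = 78 | 6 | 84/3 = 28 |

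- Rate needed: 84/26 = 3.23 per week.
- In months, at 365.25/7/12 = 4.35 weeks each: 28 weeks is 6.4 months and 42 weeks is 9.7 months.
- Excess over the stated period: 28 − 26 = 2 weeks, up to 42 − 26 = 16 weeks.

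**Does the length chosen for 6 months matter?** At 3 per week, 24 weeks gives 72, 25 gives 75, 26 gives 78 and 27 gives 81. Only 28 weeks gives 84, and that is longer than 6 months.

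**What the weekly review would see.** Halfway, at week 13, a straight line to 84 stands at 42. The stated pace stands at 2 × 13 = 26 to 3 × 13 = 39.

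**Consented or randomised?** The forecast does not say which it counts. If a fraction d of consenting women is lost before the baseline visit, the consent rate needed is 84 / (26 × (1 − d)). This is 3.23 only when d = 0 and rises with any loss. The protocol gives no value for d.

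**The case against.** The strongest reply is that the sentence is a forecast and not a design parameter. The commitment to 84 is made separately and firmly in section 5.8, and neither randomisation nor analysis uses the weekly rate. The neighbouring figures are rounded, and 3.23 is close to 3, the top of the range. Much of this stands, and it limits the weight of the point. It does not remove the error: the protocol gives a range, its best value still misses, and its midpoint misses by 19 women.

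Three stronger readings are tempting, and the protocol does not support them.

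- *The trial will be underpowered.* A reader might infer this from 52-78 recruits. It would require recruitment to stop at 26 weeks, which the protocol does not say. The comparison concerned is also labelled exploratory in section 6.0, and at 3 per week the shortfall is only 6 women.
- *The outpatient fallback will fail to start.* A reader might take its trigger to be the 2-3 per week pace. The preceding forecast names the target sample size, so reading the trigger as progress towards 84 is at least as natural. The wording leaves this open; it does not show that the fallback is broken.
- *The pace was worked out before the 30% inflation.* It does fit 64 women (64/26 = 2.46 per week), but the protocol does not say so.

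Nor is there a conflict with the 20% criterion. If all 245 women are the denominator (an assumption, since none is stated), 52 is 21% and 84 is 34%, so both lie above that floor.

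**Conclusion.** The point holds as an internal arithmetic contradiction of modest weight. Over 26 weeks the stated pace gives 52-78 women, which is 6 to 32 fewer than 84. Put the other way, the stated period is 2 to 16 weeks too short for the stated pace. The lower figures apply at 3 per week and the higher at 2 per week.

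The conclusion assumes a constant pace and counts every recruited woman towards the 84. If the rate refers to consent, any loss before the baseline visit widens the gap. The practical consequence is a timeline and a weekly benchmark that do not lead to the planned sample. The design and analysis themselves are not affected.

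**What to change.** Restate section 5.9 so that the three numbers agree, in one of two ways:

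- keep 6 months and state at least 3.23 randomised women per week over 26 weeks of accrual, with a higher consent rate to cover loss before the baseline visit; or
- keep 2-3 per week and state a recruitment period of about 28 to 42 weeks.

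In either case, say whether the rate counts consented or randomised women, and say that the targets behind the outpatient fallback are judged against the corrected accrual line to 84. The protocol offers no figure to show that 3.23 per week is achievable, so the first option needs support from the sponsor's own experience.

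If the period is lengthened, add to section 4.1a that the 20% recruitment criterion still refers to the first 6 months; otherwise its window no longer matches the recruitment period.

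The cost is a few sentences and either a more demanding stated pace or a recruitment period 2 to 16 weeks longer. The sample size, the feasibility threshold and the analysis do not change.
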